18.4. Review of Serious Adverse Events

The Chief Investigator (or designated representative) will assess all reported SAEs for causality and expectedness (NB. The Chief Investigator cannot down-grade the Principal Investigator's assessment of causality).

SAEs assessed as having a causal relationship to pembrolizumab and as being unexpected (SUSARs) will undergo expedited reporting to the relevant authorities and all other interested parties by ICR-CTSU (see below).

Sites should respond as soon as possible to requests from the Chief Investigator or designated representative (via ICR-CTSU) for further information that may be required for final assessment of an SAE.

18.5. Expedited reporting of SUSARs

If an SAE is identified as being a SUSAR by the Chief Investigator, and is fatal or life threatening, it will be reported by ICR-CTSU to the MHRA, the REC, the Sponsor, Merck, Sharp & Dohme and all other interested parties within 7 days of being notified of the event.

If an SAE is identified as a SUSAR by the Chief Investigator, and is not fatal or life threatening, it will be reported by ICR-CTSU to the MHRA, the REC, the Sponsor and Merck, Sharp & Dohme within 15 days of ICR-CTSU being notified of the event.

ICR-CTSU will report any additional relevant information to the MHRA, REC, the Sponsor and Merck, Sharp & Dohme as soon as possible, or within 8 days of the initial report of a fatal/life threatening SUSAR.

The Principal Investigators at all actively recruiting sites will be informed of any SUSARs occurring within the trial at appropriate intervals.

18.6. Follow up of Serious Adverse Events

SAEs should be followed up until clinical recovery is complete or until disease has stabilised. SAE outcomes should be reported to ICR-CTSU using the relevant section of the SAE form as soon as the Principal Investigator or designee becomes aware of the outcome.

18.7. Annual reporting of Serious Adverse Reactions

[figure not shown]
An annual report will be provided to the MHRA and the main REC by ICR-CTSU and copied to the Sponsor at the end of the reporting year.

18.8. Reporting pregnancies

Patients who become pregnant during ctDNA surveillance should stop ctDNA surveillance and be followed up as per protocol. Pregnancy during the ctDNA surveillance period should be reported to the ICR-CTSU via the deviation form, the pregnancy reporting form should not be completed.

If any trial patient or a trial participants' partner becomes pregnant while receiving trial drug or up to 120 days after receiving pembrolizumab, this should be reported to ICR-CTSU immediately using the pregnancy reporting form. Participants who become pregnant should discontinue from pembrolizumab immediately. Pregnancies should be followed up until conclusion and all follow-up information should be reported to ICR-CTSU. If the outcome of the pregnancy meets the definition of serious (i.e. congenital abnormality) this should be reported to ICR-CTSU following the serious adverse event reporting procedures described above. All reported pregnancies and follow up information (whether related to an SAE or not) will be forwarded to Merck, Sharp & Dohme upon receipt at ICR-CTSU.

Figure 2: Flow diagram for SAE reporting, and action following report

NB. All SAEs should continue to be followed up as specified above

19. STATISTICAL CONSIDERATIONS

19.1. Statistical design and sample size justification

19.1.1. Screening component

This consists of a single cohort who will have ctDNA surveillance every 3 months for 2 years. Patients who are found to be ctDNA positive within the first 12 months of ctDNA surveillance will enter the therapeutic trial. The size of the screening cohort has been chosen to anticipate the required number of patients eligible for the therapeutic trial (assuming 30% patients have a positive ctDNA during the first 12 months) and will provide further descriptive information relating to ctDNA incidence and lead time over detection of overt clinical relapse. The trial aims to recruit 150 patients into ctDNA surveillance. It is anticipated that approximately 75% of patients initially enrolled will be eligible for ctDNA surveillance, therefore approximately 200 patients will be recruited in total. The Independent Data Monitoring Committee (IDMC) will monitor the ctDNA positivity rate observed throughout the course of the trial and make recommendations regarding any increase or decrease in the overall size of the screening cohort based on this. All patients who enter the screening cohort will have the opportunity to enter the intervention phase if they become ctDNA positive within the first 12 months, regardless of the overall number of patients currently recruited to the therapeutic component of the trial.

If the incidence assumptions are correct and approximately 30% of patients have a positive ctDNA during the first 12 months of surveillance then 150 patients will enable the incidence of ctDNA positivity to be estimated with a two-sided 95% confidence interval of +/-7.3%.

In the original randomised trial design (prior to the implementation of protocol v6.0) the planned exploratory analyses were detailed as follows: Exploratory analysis will be performed comparing time to macroscopic relapse between two groups, 1) patients who remain ctDNA negative within the first 12 months and do not enter the therapeutic trial, and 2) patients who become ctDNA positive and are randomised to the observation group in therapeutic trial.

Subsequent to the removal of the randomised component (implementation of protocol v6.0) the above analyses will be amended to censor any patient who had been previously randomised to the observation group at the date they subsequently started pembrolizumab.

Under the original randomised study design (prior to protocol v6.0), of 150 patients screened, approximately 70% will remain ctDNA negative and 10% will be allocated to the observation group in the therapeutic trial (with the remaining 20% allocated to pembrolizumab in the therapeutic trial). Therefore assuming a 7:1 allocation ratio between groups 1) and 2) described above, a hazard ratio of 3.02 (assuming a reduction in 2 year relapse free rate from 80% to 51%) can be detected with 80% power, alpha 5% (two sided). We note that the HR demonstrated in retrospective testing for the ctDNA assay was 13.6, and the trial will be well powered for prospective validation.

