Circulating tumour DNA (ctDNA) represents a "liquid biopsy" alternative to invasive tumour biopsies, allowing for sensitive and specific serial sampling to be performed during the course of treatment[3]. Circulating DNA fragments carrying tumour specific sequence alterations (ctDNA) are found in the cell-free fraction of blood [4]. ctDNA can be detected in the plasma of patients with advanced cancer and can be used to track progress of disease [3, 5]. Detection of ctDNA requires highly sensitive assays due to the small proportion of ctDNA compared to the total circulating DNA [5]. Advances in sequencing technologies have enabled the rapid identification of somatic genomic alterations in individual tumours, and these can be used to design personalised assays for the monitoring of ctDNA [4]. Studies have shown the feasibility of using ctDNA to monitor tumour dynamics and in a proof-of-concept trial ctDNA was detected in 97% of metastatic breast cancers and provided an earlier measure in treatment response compared to Ca15-3 and circulating tumour cells[4, 5].

Recent work has shown that ctDNA analysis can be used to predict who is at risk of relapse [6]. In patients who have completed treatment for early breast cancer the subsequent detection of ctDNA is highly predictive for future relapse. A retrospective study of 20 primary breast cancers showed serial monitoring of ctDNA provided an average lead-time of 11 months over clinical detection of metastasis and was found to be a predictor of poor disease-free and overall survival[3].

In a prospective cohort of 55 early breast cancer patients detection of ctDNA in plasma after completion of apparently curative treatment, either at a single postsurgical time point or with serial follow-up plasma samples, predicted metastatic relapse with high accuracy. [Figure 1, hazard ratio, 13.6 (confidence interval, 4.5 to 41.2; log-rank P < 0.001) or 25.7 (from analysis using ctDNA status as a time-dependent covariate,

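### The only relapse comparison of ctDNA-positive with ctDNA-negative patients uses groups defined by later ctDNA results, so immortal time can bias the hazard ratio either way, and its 80% power at HR 3.02 is optimistic and not restated for v6.0

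*Protocol*

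**What the plan says.** Protocol section 19.1.1 sets out an exploratory comparison of time to macroscopic relapse. Group 1 is "1) patients who remain ctDNA negative within the first 12 months and do not enter the therapeutic trial". Group 2 is "2) patients who become ctDNA positive and are randomised to the observation group in therapeutic trial". Of 150 patients in surveillance, "approximately 70% will remain ctDNA negative and 10% will be allocated to the observation group in the therapeutic trial". With seven patients in group 1 for each one in group 2, the section then claims that "a hazard ratio of 3.02 (assuming a reduction in 2 year relapse free rate from 80% to 51%) can be detected with 80% power", at a two-sided 5% level. The paragraph ties this figure to the design before v6.0. It adds that retrospective testing gave a hazard ratio of 13.6, so that the trial will be well powered for prospective validation.

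For v6.0 the section keeps the analysis and makes one change: observation patients are censored at the date they start pembrolizumab. It states no time origin, no landmark and no rule for a patient who relapses before month 12 without a positive test. Power is not restated.

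Section 1.1 describes the supporting cohort. Its hazard ratio of 13.6 is for a single post-surgical sample. Its serial-sample hazard ratio of 25.7 comes "from analysis using ctDNA status as a time-dependent covariate", with a Mantel-Byar test.

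**The concern.** A patient can enter group 2 only by being relapse-free until the positive sample, so the time before detection is event-free by construction. Group 1 can be read as everyone without a positive result, including early relapses, or as those who were relapse-free and negative for the whole year. The second reading gives group 1 a guaranteed event-free year. Censoring at pembrolizumab start removes neither problem.

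The first primary objective asks whether ctDNA predicts who is at highest risk of relapse. The surveillance primary endpoint is a proportion positive. Lead time (section 19.3.2) concerns positives only. Exploratory endpoint 3 (section 19.3.3) describes lead time by clinical and biological factors, and endpoint 4 compares treated patients with and without clearance. The section 19.1.1 analysis is therefore the only specified comparison of relapse between ctDNA-positive and ctDNA-negative patients. A biased hazard ratio there would distort the evidence on that objective.

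**Working it through.** **1. The plan's own power figure.** Inputs from section 19.1.1: 105 v 15 patients (70% and 10% of 150), two-year relapse-free rates of 80% and 51%, two-sided 5%.

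- Hazard ratio: ln 0.51 / ln 0.80 = 3.02, as stated.
- Expected events by two years: 105 × 0.20 + 15 × 0.49 = 28.35.
- Freedman, with k = 1/7: d = (1.960 + 0.842)² (1 + k·HR)² / [k (HR − 1)²] = 7.849 × 2.049 / 0.583 = 27.6 events.
- Power at 28.35 events: Φ(√(28.35/7) × 2.02/1.431 − 1.96) = Φ(0.88) = 81%.

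So the 80% reproduces.

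**2. Simulated power, fixed groups, exponential times, two years' follow-up.**

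| Situation, HR 3.02 unless stated | Power |
|---|---|
| 105 v 15 (20,000 runs) | 71% |
| 105 v 10, 8 or 5 | 60%, 54%, 44% |
| 105 v 15, group 2 all censored at 12, 6 or 3 months | 52%, 36%, 24% |
| HR 13.6, 15 or 5 in group 2 | above 99% |

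The smaller group sizes and the censoring times are assumptions; the protocol gives neither.

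**3. Size of the immortal-time bias.** Hazard while ctDNA negative: λ = −ln(0.80)/2 = 0.1116 per year. Assumed detection pattern: 10% at month 0 and 5% at each of months 3, 6, 9 and 12. This totals 30%, the positivity rate the section assumes, but the spread over visits is not a protocol figure. The hazard becomes HR × λ at detection, and follow-up ends at month 24. With p the detection probability at visit time v (years), per patient in surveillance:

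- Event-free time before detection among those who turn positive: Σ p·v·e^(−λv) = 0.1150 years.
- Positive-state events and time: 0.0466 and 0.4178 years at HR 1.0; 0.1181 and 0.3504 years at HR 3.02.
- Group 1 including early relapses: 0.1534 events in 1.2597 years, rate 0.1218.
- Group 1 required to be relapse-free to 12 months, per member: 1 − e^(−λ) = 0.1056 events in 1 + 0.1056/0.1116 = 1.946 years, rate 0.0542.

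Randomising one third of positives to observation leaves these rates unchanged. The event-rate ratios are:

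| Clock and group 1 rule | True HR 1.0 | True HR 3.02 |
|---|---|---|
| Both groups from surveillance start | 0.0875/0.1218 = 0.72 | 0.2537/0.1218 = 2.08 |
| Same, negatives relapse-free to 12 months | 0.0875/0.0542 = 1.61 | 0.2537/0.0542 = 4.68 |
| Same, positives also timed from detection | 0.1116/0.0542 = 2.06 | 0.3369/0.0542 = 6.21 |
| Time-dependent ctDNA status | 1.00 | 3.02 |

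In the first two rows the positive rate is 0.0466/(0.4178 + 0.1150) = 0.0875 or 0.1181/(0.3504 + 0.1150) = 0.2537. In the last row the negative rate is 0.1534/(1.2597 + 0.1150) = 0.1116.

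A Cox fit of the second row gives 1.64 and 5.03. Other assumed detection patterns move the true 3.02 to about 1.7–2.4, 3.9–5.6 and 7–8 in the first three rows.

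**4. Error rates.** In trials of 150 patients simulated under two detection patterns, the versions that require negatives to be relapse-free to 12 months reject a true HR of 1.0 in the harmful direction 12–35% of the time. At HR 3.02 the rejection rate over all fixed-group versions runs from 28% to 93%.

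**The case against.** Several points on the other side stand.

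- The analysis is labelled exploratory, which limits its weight.
- Section 19.1.1 states no time origin, and section 19.4 leaves further methods to a statistical analysis plan that is not at hand. A landmark or delayed-entry analysis is therefore not excluded. But the protocol itself fixes the two groups, and removing the bias means departing from them or adding a rule it does not contain.
- A reader might infer that the 80% is a calculation error. It is not: it follows from Freedman's formula and is expressly confined to the original design. Schoenfeld's formula gives 49% (59 events needed), but the simulation shows this is too pessimistic at 7:1, and it should not be quoted as the true power.
- A reader might also infer that the well-powered remark is false. It refers to a hazard ratio of 13.6, at which power stays above 99% even with 5 observation patients in fixed groups followed for two years. The reassurance is limited because 13.6 came from one post-surgical sample, not from status over 12 months.
- Leaving out the post-detection time of pembrolizumab-allocated patients might look like waste. It protects the comparison. They are scanned on a positive result (sections 3.2.1, 11.1 and 11.7), while observation patients were followed blinded in the same way as negatives (section 9). Take 30 such patients with 4 weeks each, or 2.3 person-years: HR 3.02 predicts 2.3 × 0.1116 × 3.02 = 0.8 events. If scans found disease in 10% (an assumption), 3 events would give an apparent hazard ratio near 12.

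**Conclusion.** The concern holds in a qualified form. Both groups are defined by results after surveillance starts, no remedy is stated, and the resulting bias can run either way. Under the assumed detection pattern, a true hazard ratio of 1.0 appears as about 0.7, 1.6 or 2.1, and 3.02 as about 2.1, 4.7 or 6.2, depending on choices the section leaves open. The exact values rest on that pattern and on constant hazards. The documents do not support saying that the bias always inflates the effect or always lowers power.

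On power, the 80% at HR 3.02 is an optimistic approximation: about 71% by simulation for the original design. It is lower under v6.0, by an amount the protocol does not allow one to fix. The change should be made, but the analysis is exploratory and a very large true effect would still be detected.

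**What to change.** Replace the two-group comparison in section 19.1.1 with ctDNA status as a time-dependent covariate (Mantel-Byar or Cox), timed from surveillance start:

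- All surveillance patients contribute ctDNA-negative time until their first positive sample.
- A relapse with no prior positive sample counts as a ctDNA-negative event.
- Observation patients switch to positive at that sample. In the analysis they are censored when allocated to pembrolizumab under v6.0, before the staging scan this triggers.
- Pembrolizumab-allocated patients are censored at their first positive sample, so that scan-triggered detection does not inflate the hazard ratio.

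Restate the 80% as about 71% for the original fixed-group design and give the power for the observation patients actually randomised, or delete the claim.

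The cost is wording, fewer positive-state events and a less favourable power figure. With one third of positives in observation and two years' follow-up, the time-dependent analysis has simulated power at HR 3.02 of about 66% if detection is mostly at baseline and 54% if it is spread over the year (both patterns assumed). No new data are needed.

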19.1.2. Therapeutic component

Under the original randomised study design (prior to protocol v6.0), those patients allocated via randomisation to observation provide a reference control rather than a formal randomised comparator group. The statistical considerations underpinning the therapeutic intervention evaluation are those of a single group trial with patients treated with pembrolizumab in both the randomised and non-randomised

trial components combined. The original design hypothesised frequencies of ctDNA+ and allocation to pembrolizumab as per the text and table outlined below. The revision in the design to close the randomised component has the potential to increase the number of patients commencing pembrolizumab. No redefinition of the criteria have been undertaken since the success criteria are determined by the number starting treatment and not the overall proportion available to receive treatment.

The rate of ctDNA positivity is prone to stochastic effects, and as such a range of effect sizes is presented. All patients in the screening cohort who are observed to have a positive ctDNA will be entered into the therapeutic component, therefore the eventual number entering that phase will only be defined as the trial progresses. The most likely incidence, on which the primary calculations were made, is for a 30% positivity rate during the first 12 months. Calculations use an A'Hern single-stage design within pembrolizumab treated patients, alpha=0.1, power=90%, unacceptable ctDNA clearance rate p0 (of 0.3) and minimum required level of efficacy p1 of approximately 0.5. The number of clearances to conclude the required level of success and width of the 95% confidence interval which could be detected around a proportion with ctDNA clearance of approximately 0.5 are given for each hypothesised rate of ctDNA positivity.

Rate of ctDNA positivity	No. ctDNA positive (of 150 in ctDNA surveillance phase)	No. randomised to receive pembrolizumab	р0	р1	No. successes required	Width of 95% confidence interval detectable around proportion of 0.5
45%	68	45	0.30	0.49	18	+/- 0.14
30%	45	30	0.30	0.54	13	+/- 0.17
24%	36	24	0.30	0.57	10	+/- 0.19

In prior research no patients with ctDNA detected at baseline spontaneously cleared ctDNA thus it is anticipated that such clearance would demonstrate activity of the intervention. The reference group in the randomised component of the trial will however provide further evidence to support that assertion. The number of patients randomised to the observation group (prior to the implementation of protocol v6.0) who have spontaneous clearance will be recorded and will be presented together with an associated 95% confidence interval to illustrate the likely theoretical upper bound of such an occurrence. Patients who subsequently receive pembrolizumab after transitioning to the non-randomised component of the trial will be excluded from this analysis if they start treatment within 24 weeks of becoming ctDNA positive and are therefore not assessable for the ctDNA clearance endpoint.

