3.2.1. Pembrolizumab treatment group

If a patient is allocated to the pembrolizumab treatment group, the treating team will be informed by ICR-CTSU. If the patient is receiving adjuvant capecitabine or radiotherapy, they will be offered the option to join the therapeutic trial either by switching treatment from capecitabine to pembrolizumab, or commencing pembrolizumab in combination with radiotherapy. If the patient confirms their consent to receive trial treatment (including switching their treatment from capecitabine to pembrolizumab) staging scans should be done to detect for evidence of macroscopic disease, prior to commencing pembrolizumab. If macroscopic disease is detected, the patient will not receive pembrolizumab treatment and will instead receive standard treatment for recurrent disease outside of the c-TRAK TN trial. If there is no evidence of macroscopic disease, the patient should commence treatment with pembrolizumab treatment (200mg given intravenously every 3 weeks) for up to a maximum of 12 months or until unacceptable toxicity or withdrawal of the patient's consent for any reason (see section 11.6). No further imaging will be performed after commencing pembrolizumab unless clinically indicated, in which case local procedure should be followed. Patients who are diagnosed with disease recurrence must stop pembrolizumab, and should receive standard treatment for recurrent disease outside of the c-TRAK TN trial. Patients who present with isolated lymphadenopathy may continue pembrolizumab until relapse is confirmed, and should be managed as per section 13.1.

Patients who are allocated to pembrolizumab but do not wish to commence pembrolizumab treatment (including switching treatment from capecitabine to pembrolizumab), will not enter the therapeutic component of the c-TRAK TN trial and if agreed should instead continue with 3 monthly ctDNA surveillance. Blood samples for ctDNA analysis should continue to be collected during and after pembrolizumab treatment as described in section 11. The results of these ctDNA analyses will not be reported to the treating team or patient.

3.2.2. **Observation group (continued blinded ctDNA surveillance – prior to protocol v6.0)**

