19.3. Endpoint definitions

19.3.1. **Primary Endpoints**

ctDNA surveillance

• Positive ctDNA detection by 12 and 24 months from start of ctDNA surveillance. This will be calculated as the proportion of patients with ctDNA positivity by each time point from those with assessment performed at that time point. Proportions will be presented with associated exact 95% confidence intervals.

Therapeutic component

 Absence of detectable ctDNA or disease recurrence 6 months (24 weeks) after commencing pembrolizumab. This will be calculated as the proportion of patients without either detectable ctDNA or disease recurrence 6 months after commencing pembrolizumab. Proportions will be presented with associated exact 95% confidence intervals.

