19.3.2. Secondary Endpoints

Secondary endpoints relating to the observation group will be analysed in the patients randomised to the observation group prior to the implementation of protocol v6.0.

ctDNA surveillance

1) Time to ctDNA detection. This will be calculated as the time from entry into the ctDNA surveillance to first positive ctDNA detection. Statistical techniques for time to event data will be used to summarise data and display the pattern of ctDNA detection graphically.

Therapeutic component

- Detection of overt metastatic disease at the time of first ctDNA detection in patients allocated to pembrolizumab. This will be calculated as the proportion of patients with metastatic disease from CT scan at the same time point as first positive ctDNA detection, and presented with associated exact 95% confidence interval.
- 2) Lead-time between ctDNA detection and recurrence in the pembrolizumab treatment and observation groups. This will be calculated as the time between therapeutic trial entry and first confirmed detection of recurrent disease. Recurrence will include loco-regional and distant recurrence, but will exclude new primary cancers. Statistical techniques for time to event data will be used to summarise data and display time between ctDNA detection and recurrence graphically.
- 3) Absence of detectable ctDNA or disease recurrence after 6 months in the observation group. This will be calculated as the proportion of patients without either detectable ctDNA or disease recurrence 6 months after randomisation to the observation group. Proportions will be presented with associated exact 95% confidence intervals.
- **4)** Safety and tolerability of pembrolizumab in this patient group. Safety will be assessed throughout the treatment period using the NCI CTCAE v4.0 and summarised in tabular format. Reported toxicities

will be coded using Med DRA (current version). The proportion of patients reporting a dose reduction/delay during pembrolizumab will be presented.

5) Commencement of treatment in patients allocated to receive pembrolizumab. This will be calculated as the proportion of patients allocated to receive pembrolizumab who start this therapy. The proportion will be presented with associated exact 95% confidence interval.

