19.4. Statistical Analysis Plan

In the therapeutic component of the trial, analyses will be performed using the intention to treat (ITT) population meaning patients who do not meet the eligibility criteria (for reasons other than disease recurrence) or do not wish to receive pembrolizumab treatment will still be included in the analysis of the primary endpoint (ctDNA clearance). These patients should continue to have bloods taken for ctDNA surveillance every 3 months for up to 2 years from starting ctDNA surveillance. Patients will then be followed up until disease recurrence detection. Sensitivity analyses will also be performed using a per-protocol

population including only patients who start pembrolizumab treatment. If large differences are observed between ITT and per-protocol analyses, both results will be presented and reasons for failure to start pembrolizumab (ineligibility, patient choice) further explored.

All analysis will be repeated in the subset of patients who enter into the study within the recruitment time windows of protocol version 5.0, and the subset of patients who enter the study outside the recruitment time windows of protocol version 5.0. Further details of analysis methods will be specified in a Statistical Analysis Plan in accordance with ICR-CTSU Standard Operating Procedures.

The Statistical Analysis Plan will include a section to detail how data impacted by strategies introduced to mitigate risks relating to the COVID-19 pandemic will be handled.

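### The observation clearance rate, used as evidence that clearance reflects drug activity, is not like-for-like with the pembrolizumab rate, and its upper bound is too tight for scan-negative patients

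*Protocol*

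**What the plan says.** **Role of the observation group.** Section 19.1.2 of the protocol states: "The statistical considerations underpinning the therapeutic intervention evaluation are those of a single group trial". Observation patients "provide a reference control rather than a formal randomised comparator group". The test is an A'Hern single-stage design with "alpha=0.1, power=90%, unacceptable ctDNA clearance rate p0 (of 0.3) and minimum required level of efficacy p1 of approximately 0.5". The same section then says that the reference group will add support to the claim that clearance demonstrates activity. Its clearance count is reported with a 95% confidence interval "to illustrate the likely theoretical upper bound of such an occurrence".

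**The two clearance endpoints.**
- Pembrolizumab (19.3.1): "proportion of patients without either detectable ctDNA or disease recurrence 6 months after commencing pembrolizumab".
- Observation (19.3.2, therapeutic item 3): "proportion of patients without either detectable ctDNA or disease recurrence 6 months after randomisation to the observation group".

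**Who is counted.**
- Allocation to pembrolizumab leads to staging scans. "If macroscopic disease is detected, the patient will not receive pembrolizumab treatment" (3.2.1; 9.3 agrees).
- The intention-to-treat set for the primary endpoint (19.4) keeps patients who decline and "patients who do not meet the eligibility criteria (for reasons other than disease recurrence"). By implication, those ineligible because of recurrence are left out.
- Before v6.0, observation patients and their teams were not told of the positive result (3.2.2, section 9), so no scan followed from it.
- Observation patients who start pembrolizumab within 24 weeks of becoming ctDNA positive are excluded from the observation clearance analysis (19.1.2).

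**Comparison by randomised group.** The only one is descriptive and covers time to recurrence and disease-free survival (19.3.3, item 1). Clearance is not included.

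**The concern.** A reference rate for spontaneous clearance should describe the kind of patient in whom clearance on the drug is counted. Here it does not. A patient with overt but unrecognised disease at detection leaves the pembrolizumab analysis after the trigger scan. The equivalent observation patient is not scanned, stays in the denominator and will almost certainly fail. Section 1.2.1 says that overt metastatic disease has turned out more frequent than expected, so the mismatch may not be small.

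At stake is the supporting argument, not the primary decision. A reader who sets the observation rate or its upper limit beside the pembrolizumab rate is comparing two differently selected groups. Patients were randomised between these options before v6.0, so a like-for-like estimate could be reported, but the protocol does not ask for one.

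**Working it through.** **1. The plan's own rule.** Inputs from the main row of the 19.1.2 table: n = 30, p0 = 0.30, p1 = 0.54, 13 successes. Exact binomial tails give P(X ≥ 13) = 0.084 at 0.30 and 0.912 at 0.54. This meets alpha 0.1 and power 90%. The observation rate does not enter the rule.

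**2. Planned observation group.** Section 19.1.1 gives 10% of 150 = 15 patients.

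**3. Effect of one-sided scan selection.** Let c be spontaneous clearance in scan-negative patients and f the share with macroscopic disease at detection. The protocol does not give f; 10% to 50% is assumed. Also assume that patients with overt disease never clear. The unscanned observation rate is then c(1 − f).

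| c | f = 0.1 | f = 0.3 | f = 0.5 |
|---|---|---|---|
| 0 | 0 | 0 | 0 |
| 0.10 | 0.09 | 0.07 | 0.05 |
| 0.20 | 0.18 | 0.14 | 0.10 |

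Selection pulls the reference down unless c = 0.

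**4. Effect of dropping early crossovers.** These patients start pembrolizumab only after a further positive result, so they are mostly non-clearers. With 1 clearance and k patients dropped, the rate is 1/(15 − k): 6.7% (k = 0), 7.7% (k = 2), 9.1% (k = 4), 11.1% (k = 6). This pushes the reference up.

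**5. Net direction.** If all k dropped patients are non-clearers, the reported rate is c(1 − f)/(1 − k/15). It is below c when k/15 < f and above c when k/15 > f. With c = 0.20 and f = 0.3, the expected number of clearances is 15 × 0.14 = 2.1. With k = 4 the rate is 2.1/11 = 19.1%; with k = 6 it is 2.1/9 = 23.3%. The protocol gives neither f nor k, so the sign is open.

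**6. Clocks.** Treatment should start within 4 weeks of the site being told of the allocation, with extension possible (9.3). Timing from first dose requires a patient to be free of recurrence until then, which favours pembrolizumab. It also puts the assessment later after detection, which works against it. There is no fixed direction.

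**7. The upper bound when spontaneous clearance is zero.** The exact two-sided 95% upper limit for 0/n is 1 − 0.025^(1/n).

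| Scan-negative patients among 15 | Implied f | Upper limit for 0/n |
|---|---|---|
| 15 | 0 | 21.8% |
| 12 | 0.20 | 26.5% |
| 10 | 0.33 | 30.8% |
| 8 | 0.47 | 36.9% |

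The point estimate is 0 in every row. Only the amount of information about scan-negative patients changes.

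**8. What an as-randomised comparison could show.** Take the planned 30 v 15 and Fisher's test at two-sided 5%. Trigger-scan disease counts as failure, so the proportions are 0.54(1− f) and, for an assumed 5% spontaneous clearance, 0.05(1 − f). Power is 91%, 85%, 76% and 44% for f = 0.1, 0.2, 0.3 and 0.5. Against a reference of 0.30, with 0.54 undiluted, it is only 25%. Randomisation closed early, so the real groups may be smaller than 30 and 15.

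**The case against.** The strongest objection is that the protocol openly disclaims a formal comparison, judges success only against a fixed 0.30, and nowhere subtracts one proportion from the other or tests the observation bound against 0.30. No decision changes. That stands. It does not remove the point, because 19.1.2 still uses the observation rate as supporting evidence.

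A reader might infer a stronger claim: that the reference comes from all randomised observation patients, is set against a purely scan-negative pembrolizumab group, and is therefore biased low in pembrolizumab's favour. The protocol does not support this:
- Early crossovers are dropped, so the group is not all those randomised, and dropping them raises the reference rate. They must also be scan-negative to start, so those left are more enriched for overt disease; this widens the mismatch without settling its sign.
- The intention-to-treat set keeps patients who decline or are ineligible for other reasons. Some may be unscanned, and being untreated they probably lower the pembrolizumab figure. Scan-negative strictly describes those who start.
- The clock difference has no fixed direction.
- At c = 0, the protocol's own expectation, the point estimate is not biased.

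It is also fair that 19.3.2 reports overt disease at first detection among patients allocated to pembrolizumab, and the proportion who start. Readers will therefore be able to estimate f. That helps interpretation but does not make the two rates comparable. An SAP, not available here, may add detail; the clocks and analysis sets at issue are fixed in the protocol itself.

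**Conclusion.** The point holds in a limited form. The observation clearance rate is not like-for-like with the pembrolizumab rate: scan selection acts on one side only, the clocks differ, and early crossovers are dropped from observation. A net bias in pembrolizumab's favour is not established, because these features pull in different directions and the protocol gives neither the overt-disease share nor the number of crossovers.

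The clearest consequence is for the upper bound. With zero clearances, 21.8% from 0/15 overstates what is known about scan-negative patients; 26.5% to 36.9% would apply if 12 to 8 of the 15 were scan-negative. These figures rest on the planned group size, no exclusions for crossover, and an assumed overt-disease share of 20% to about 47%. Whether the bound for scan-negative patients passes 0.30 depends on that share: at 20% it does not.

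The A'Hern decision is untouched. This is an inexpensive improvement to the supporting evidence.

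**What to change.** Keep the A'Hern test as primary. Then:

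1. In 19.3.2, therapeutic item 3, add a supportive, descriptive analysis of patients randomised before v6.0, in their randomised groups. Report the proportion ctDNA-negative and recurrence-free 24 weeks after randomisation in each group, with the difference and its exact 95% confidence interval.
2. In that analysis, count macroscopic disease on the trigger scan as failure in the pembrolizumab group.
3. Count observation patients who start pembrolizumab before the 24-week assessment as non-clearers, and add a sensitivity analysis that excludes early crossovers as 19.1.2 does. Clearance on the drug is then never credited to observation.
4. In 19.1.2, state that the upper bound describes unscanned ctDNA-positive patients and is to be read against the as-randomised pembrolizumab proportion, not the proportion among those who start.

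The cost is protocol or SAP wording and one extra analysis of data already collected. The interval will be wide because randomisation closed early, and the pembrolizumab proportion will be lower than among starters. Counting crossovers as non-clearers may slightly understate observation clearance; the sensitivity analysis shows how much this matters.
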